### **A2.3** Confirming progression

Unlike RECIST 1.1, iRECIST requires the confirmation of progression and uses the terms iUPD (unconfirmed progression) and iCPD (confirmed progression). The first confirmatory scan should be performed 6 weeks after iUPD (at least 4 weeks, but no longer than 8 weeks after iUPD).

iCPD is confirmed if further increase in tumour burden, compared to the last assessment, is seen as evidenced by one or more of the following:

- Continued increase in tumour burden (from iUPD) where RECIST 1.1 definitions of progression had been met (from nadir) in target, non-target disease or new lesions
  - Progression in target disease worsens with an increase of at least 5 mm in the absolute value of the sum
  - Continued unequivocal progression in non-target disease with an increase in tumour burden
  - Increase in size of previously identified new lesion (s) (an increase of at least 5 mm in the absolute value of the sum of those considered to be target new lesions) or additional new lesions.
- RECIST 1.1 criteria are met in lesions types (target or non-target or new lesions) where
  progression was not previously identified, including the appearance of additional new lesions.

If iUPD is not confirmed at the next assessment, then the appropriate response will be assigned (iUPD if the criteria are still met, but no worsening, or iSD, iPR or iCR if those criteria are met compared to baseline). As can be seen in table 2, the prior documentation of iUPD does not preclude assigning iCR, iPR, or iSD in subsequent time-point assessments or as best overall response (BOR) providing that iCPD is not documented at the next assessment after iUPD.

### A2.4 New lesions

New lesions should be assessed and measured as they appear using RECIST 1.1 criteria (maximum of 5 lesions, no more than 2 per site, at least 10 mm in long axis (or 15 mm in short axis for nodal lesions), and recorded as New Lesions-Target (NLT) and New Lesion-Non-Target (NLNT) to allow clear differentiation from baseline target and non-target lesions.

New lesions may either meet the criteria of NLT or NLNT to drive iUPD (or iCPD). However, the measurements of target lesions should NOT be included in the sum of measures of original target lesions identified at baseline. Rather, these measurements will be collected on a separate table in the case record form.

PD is confirmed in the New Lesion category if the next imaging assessment after iUPD confirms further progression from iUPD with either an increase of at least 5 mm in the absolute value of the sum of NLT OR an increase (but not necessarily unequivocal increase) in the size of NLNT lesions OR the appearance of additional new lesions.

A2.4.1 Time-point (TP) iResponse

A2.4.1	Time-point (TP)	ikespoi	ise	
			Time Point Response	
Target Lesions*		New Lesions*	No prior	·
iCR	iCR	No	iCR	iCR
iCR		No	iPR	iPR
iPR	Non-iCR/Non- iUPD	No	iPR	iPR
iSD	Non-iCR/Non- iUPD	No	iSD	iSD
decrease			NA	NLs confirms iCPD if NLs were previously identified and increase in size (≥5 mm in SOM for NLT or any increase for NLNT) or number. If no change in NLs (size or number) from last TP, remains iUPD
iSD	iUPD	No	:1100	Remains iUPD unless iCPD confirmed based in further increase in size of NT disease (need not meet RECIST 1.1 criteria for unequivocal PD)
iUPD	Non-iCR/Non- iUPD	No	iUPD	Remains iUPD unless iCPD confirmed based on: o further increase in SOM of at least 5 mm, otherwise remains iUPD
iUPD	iUPD	No	iUPD	Remains iUPD unless iCPD confirmed based on further increase in: opreviously identified T lesion iUPD SOM ≥5 mm and / or o NT lesion iUPD (prior assessment - need not be unequivocal PD)

iUPD	iUPD	Yes	iUPD	Remains iUPD unless iCPD confirmed based on further increase in: opreviously identified T lesion iUPD ≥5 mm and / or o previously identified NT lesion iUPD (need not be unequivocal) and /or osize or number of new lesions previously identified
Non- iUPD/PD	Non-iUPD/PD	Yes	Non- iUPD/ PD	Non-iUPD/PD

\* Using RECIST 1.1 principles. If no PSPD occurs, RECIST 1.1 and iRECIST categories for CR, PR and SD would be the same. \*\* In any lesion category. \*\*\* Previously identified in assessment immediately prior to this TP.

All patients will have their iBOR from the start of study treatment until the end of treatment classified as outlined below.

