## 4.2. Secondary endpoints

- Response according to iRECIST
- Clinical benefit at 9 weeks after starting study treatment (CR/PR/SD according to RECIST v1.1)
- Best response up to 6 months according to RECIST v1.1 and iRECIST
- Duration of response
- Time to progression
- Progression free survival
- Overall survival
- Treatment related toxicity
- Patient reported quality of life, assessed using the EORTC QLQ-C30 (32) & EQ-5D-5L (33)

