#### 8.6. Procedure at RECIST v1.1. progression for patients continuing treatment

Participants who continue treatment post RECIST v1.1 progression should continue to be followed up according to the schedule above, with CT scans scheduled as described below (also see Appendix A4).

- A CT CAP for the purposes of iRECIST assessment should be conducted 6 weeks following confirmation of progressive disease according to RECIST v1.1.
- Should the patient continue on treatment following their first iRECIST assessment, subsequent CT CAP should be conducted for further iRECIST assessment at the following intervals:
  - o 12 weeks after first iRECIST assessment
  - Every 9 weeks thereafter in the first year post start of study treatment, then every 12 weeks in the second year
- Translational sub-study samples (if participating): EDTA 10ml x 3, Tempus 3ml and Streck 10ml should be taken at RECIST v1.1 progression. If progression occurs at the primary endpoint bloods only need to be taken once.

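### After iUPD, first progression in another lesion category is iCPD under A2.3, but the iUPD/iUPD/Yes row of A2.4.1 keeps it at iUPD when the earlier categories have not worsened

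*Protocol*

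**What the plan says.** Protocol Appendix A2.3 lists criteria for iCPD, any one of which is enough. One is continued increase in disease that had already progressed. A separate one is RECIST 1.1 progression in a lesion type where "progression was not previously identified, including the appearance of additional new lesions"; it does not require the earlier category to worsen. If progression is not confirmed, A2.3 assigns "iUPD if the criteria are still met, but no worsening". A later iCR, iPR or iSD may still be assigned, "providing that iCPD is not documented at the next assessment after iUPD".

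Table A2.4.1 codes each time point. Two rows have both target and non-target disease at iUPD, one without and one with new lesions. In each, the right-hand cell keeps iUPD unless there is a further increase in a listed item:

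- **No new lesions (No row):** the target iUPD already identified, by at least 5 mm, and/or "NT lesion iUPD (prior assessment - need not be unequivocal PD").
- **New lesions (Yes row):** the target iUPD already identified, by at least 5 mm, and/or "previously identified NT lesion iUPD (need not be unequivocal"), and/or the size or number of new lesions already identified.

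Neither cell lists first progression in another category. No sentence in the available text says which prevails, A2.3 or the table.

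**The concern.** Two written rules for the same scan can give different codes, and sites apply them in real time.

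- **Treatment:** under section 8.8, iCPD is the point at which atezolizumab is expected to stop, and continuing calls for discussion with the Chief Investigator. iUPD triggers neither.
- **Scanning:** under footnote 7 of section 8.10, iRECIST scans run until iCPD or treatment discontinuation.
- **Best overall response under iRECIST (iBOR):** in A2.4.2, iUPD followed directly by iCPD gives an iBOR of iCPD whatever comes later. If the scan stays iUPD, A2.3 lets a later iPR or iCR count.

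An SAP rule could harmonise the derived codes afterwards, but it could not undo a stopping or scanning decision already made on site.

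**Working it through.** The main check is textual; the arithmetic only bounds timing and size.

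**1. The two rules side by side, Yes row**

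| | Week 9 | Week 15 |
|---|---|---|
| Target | iUPD | sum unchanged, so still iUPD |
| New lesion | present | unchanged |
| Non-target | not progressing | first unequivocal progression |

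- A2.3: non-target is a lesion type not previously progressing, so its second route is met. Code: iCPD.
- A2.4.1, Yes row: the target sum has not increased, the new lesion has not grown or multiplied, and there was no earlier non-target iUPD to increase. Code: iUPD.

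The result rests on this pattern. Other orders are not relied on. For example, where target disease progresses second, a reader could apply the 5 mm test to any target growth and reach iCPD under both texts.

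**2. The No row**

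Week 9: target iUPD only. Week 15: target unchanged, first non-target progression, no new lesion. A2.3 gives iCPD. The table depends on the words prior assessment:

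- If they mean that the non-target iUPD must already have existed, the code is iUPD and the texts conflict.
- If they name the scan against which increase is judged, as A2.3 does when it compares with the last assessment, first unequivocal progression more than meets the test. The code is iCPD and the texts agree.

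**3. Timing against best response**

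Section 4.2 lists "Best response up to 6 months according to RECIST v1.1 and iRECIST". A2.3 sets the confirmatory scan at 6 weeks, "at least 4 weeks, but no longer than 8 weeks after iUPD". Section 8.6 puts the next one "12 weeks after first iRECIST assessment".

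- iUPD at week 9: confirmatory scan at 9 + 6 = week 15 (13 to 17); next at 15 + 12 = week 27 (25 to 29).
- Six months = 182.6 / 7 = 26.1 weeks. The next scan falls inside only if the confirmatory scan is done by 26.1 − 12 = 14.1 weeks.
- iUPD at week 18: weeks 24 and 36, so the later scan is outside.

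At the disputed scan itself both codes are non-responses, so best response to six months is largely unaffected.

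**4. Size, as a break-even**

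Inputs: 92 evaluable patients, so 46 per arm (section 12.1); in IMvigor210, 121 of 310 continued past progression and 17% of those later responded (section 1.1). It is an assumption that these figures carry over.

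- Late responders per arm: 121/310 × 46 × 0.17 = 3.05.
- Share needing the disputed pattern to change one response: 1 / 3.05 = 33%.
- If 30% continue: 0.30 × 46 × 0.17 = 2.35, so 43%. If 50% continue: 3.91, so 26%.
- One response = 1/46 = 2.2 percentage points.

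The true share is probably far lower. A1.5 describes unequivocal non-target progression as enough added burden to justify stopping therapy, so many such patients would stop under either code.

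**The case against.** **A2.3 is the rule section.** Its title and its any-one-suffices structure suggest that it governs, with the cells merely describing persistence in categories already progressing. On that view the table is incomplete, not a rival rule. This is a sensible way to resolve the conflict, but the cells are worded as an instruction to keep iUPD unless listed conditions hold, and a site coding from the table has no stated reason to look past it.

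**The No row.** A reader might infer that both rows contradict A2.3 outright. The No row does not support that: its non-target clause lacks the words previously identified that the Yes row uses, and its reference to the prior assessment can be the comparator. This objection stands; the No row is ambiguous.

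**Legibility.** The header of the right-hand column is lost in the extracted text. That the column covers prior iUPD is inferred from the cell wording. A footnote ties previously identified to the immediately preceding assessment, but its marker in the table is also lost, so it supports the reading without settling it. Appendix A4, the treatment and scan algorithm, appears only as a heading, so the absence of a precedence rule is established only for the text that can be read.

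**Endpoint effect.** A reader might infer that the iRECIST objective response comparison changes. Section 12.3.2 gives that endpoint no time point, but section 12.4 compares it in the same way as the primary endpoint, which is fixed at week 9. If that includes the timing, a disputed scan at about week 15 cannot affect it. This also stands: the effect is possible, not shown.

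**Treatment effect.** Atezolizumab stops on loss of clinical benefit in any case, and section 8.8 allows continuation after iCPD with the Chief Investigator's agreement. The code changes what is expected and who is consulted; it does not dictate the outcome.

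**Conclusion.** The point holds as a minor inconsistency. The Yes row of A2.4.1, read literally, gives a different code from A2.3 when a further category progresses and the earlier ones have not worsened. The No row probably does the same but can be read consistently with A2.3.

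The direct effect is on a few patients' iUPD or iCPD codes, and through them on the discontinuation and discussion trigger, continued iRECIST scanning and iBOR, which runs to the end of treatment. In A2.4.2 the only row beginning iUPD, iUPD ends in iCPD, so the permission for a later response to count comes from A2.3. iRECIST objective response could change only if it is not tied to week 9. The number of changed responses cannot be estimated from the protocol; below one per arm is a judgement, supported by the break-even shares of 26% to 43%.

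A reader might go further and infer bias between arms or a threat to the main result. The documents support neither. The same rules apply in both arms, and the primary endpoint, futility rule and sample size rest on RECIST v1.1 response at 9 weeks.

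**What to change.** State in Appendix A2 that A2.3 governs wherever it and table A2.4.1 differ. In the prior-iUPD cells of both iUPD/iUPD rows, add a further route to iCPD: RECIST 1.1 progression in any lesion category (target, non-target or new lesions) that was not progressing before. Derive iCPD by that rule in both arms. The clause also removes the ambiguity in the No row.

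The cost is one sentence and one clause in two table cells, with no new data, scans or patients.

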# A2.4.2 iRECIST best overall response (iBOR)

		•	•		
TPR1	TPR2	TPR3	TPR4	TPR5	iBOR
iCR	iCR, iPR,	iCR, iPR, iUPD, NE	iUPD	iCPD	iCR
	iUPD, NE				
iUPD	iPR, iSD, NE	iCR	iCR, iPR, iSD, iUPD, NE	iCR, iPR, iSD, iUPD, iCPD, NE	iCR
iUPD	iPR	iPR, iSD, iUPD, NE	iPR, iSD, iUPD, NE, iCPD	iPR, iSD, iUPD, NE, iCPD	iPR
iUPD	iSD, NE	PR	iPR, iSD, iUPD, NE	iPR, iSD, iUPD, iCPD, NE	iPR
iUPD	iSD	iSD, iUPD, NE	iSD, iUPD, iCPD, NE	iSD, iUPD, ICPD, NE	iSD
iUPD	iCPD	Anything	Anything	Anything	iCPD
iUPD	iUPD	iCPD	Anything	Anything	iCPD
iUPD	NE	NE	NE	NE	iUPD

Table assumes a randomised study where confirmation of CR or PR is not required.

NE = not evaluable that cycle.

Designation "I" for BOR can be used to indicate prior iUPD to aid in data interpretation.

# A2.5 Response and stable disease duration (RECIST 1.1 and iRECIST)

Response duration will be measured from the time measurement criteria for CR/PR or iCR/iPR (whichever is first recorded) are first met until the first date that recurrent or progressive disease is objectively documented, taking as reference the smallest measurements recorded on study (including baseline).

Stable disease duration will be measured from the time of start of treatment until the criteria for progression are met, taking as reference the smallest sum on study (including baseline).

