#### 12.3.2. Secondary endpoints

- Objective response according to iRECIST (iCR + iPR)
- Clinical benefit at 9 weeks according to RECIST v1.1 (CR, PR, SD)
- Best response up to 6 months, defined as specified in A1.10
- Duration of response, defined as time from objective response until recurrence or progressive disease (PD)
- Time to progression, defined as time from randomisation until confirmation of progression
- Progression free survival, defined as time from randomisation until progression or death from any cause
- Overall survival, defined as time from randomisation until death from any cause
- Treatment related toxicity (CTCAE v5)

• Patient reported quality of life (assessed using the EORTC QLQ-C30 and EQ-5D-5L questionnaires) at 9 weeks and 6 months for all patients participating in the QoL substudy. In addition any QoL sub-study patients still being treated with atezolizumab at 12 months should be asked to complete the EORTC QLQ-C30 and EQ-5D-5L at this timepoint. The primary outcome measure will be overall quality of life, measured by the EORTC QLC-C30 qlobal health/QoL subscale score.

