### A1.8 Duration of overall response

The duration of overall response is measured from the time measurement criteria are met for CR or PR (whichever status is recorded first) until the first date that recurrence or PD is objectively documented, taking as reference for PD the smallest measurements recorded since the treatment started.

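### Appendix A2.5 uses one stopping rule for response duration under both RECIST v1.1 and iRECIST, so an unconfirmed progression ends an iRECIST response that A2.3 would keep open

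*Protocol*

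**What the plan says.** Appendix A2.5, whose title covers both criteria sets, gives the start of the clock as follows: "Response duration will be measured from the time measurement criteria for CR/PR or iCR/iPR (whichever is first recorded) are first met". The clock then runs "until the first date that recurrent or progressive disease is objectively documented", with the smallest measurements on study (baseline included) as reference.

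Appendix A2.3 treats progression differently under the two sets: "Unlike RECIST 1.1, iRECIST requires the confirmation of progression and uses the terms iUPD (unconfirmed progression) and iCPD (confirmed progression". It adds that "the prior documentation of iUPD does not preclude assigning iCR, iPR, or iSD in subsequent time-point assessments", provided iCPD is not documented at the next assessment.

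Appendix A1.8, the RECIST v1.1 rule, stops the clock in nearly the same terms as A2.5: "until the first date that recurrence or PD is objectively documented".

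Section 12.3.2 lists the secondary endpoint without naming a criteria set: "Duration of response, defined as time from objective response until recurrence or progressive disease (PD". The next item in that list does refer to confirmation: "Time to progression, defined as time from randomisation until confirmation of progression". Section 12.4 analyses duration of response by arm with Kaplan-Meier plots, log-rank tests and Cox models.

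**The concern.** The start in A2.5 admits iRECIST responses, but the stop is the RECIST v1.1 stop. Under iRECIST the first progression seen is only an iUPD, and it may be withdrawn at the next scan. If the clock stops there, a patient whom iRECIST still rates as a responder is counted as having lost the response.

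A second difficulty concerns patients who progress by RECIST v1.1 and respond afterwards, the late responses that section 1.5 gives as the reason for the trial. They are responders under iRECIST only. A2.5 brings them in through its start and does not say which iRECIST event takes them out.

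At stake is a secondary endpoint. Two analysts following the protocol could derive different durations and event indicators for the same patient, and the Kaplan-Meier curve for duration of response could mix two definitions.

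**Working it through.** The protocol states no figure that depends on this definition, so there is nothing to reproduce. The check applies A2.5 to scan sequences that the protocol allows.

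**Inputs**
- First on-study RECIST v1.1 scan at week 9, then every 9 weeks in the first year (section 8.4).
- After RECIST progression with treatment continued: a scan 6 weeks later, the next 12 weeks after that, then every 9 weeks in the first year (section 8.6).
- RECIST v1.1 assessment stops at RECIST progression (section 8.4). Later scans are read by iRECIST (section 8.6).
- Confirmatory scan 6 weeks after an iUPD (A2.3).

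**1. Which event does the A2.5 stop describe?** Three features point to the unconfirmed event.
- The reference is the smallest measurement on study. That is the reference for RECIST progression (A1.4) and so for iUPD. A2.3 judges iCPD by further increase since the last assessment.
- The wording follows A1.8, where no confirmation is needed.
- Section 12.3.2 mentions confirmation for time to progression and not for duration of response.

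**2. Are the affected sequences foreseen?** Yes. The table in A2.4.2 allows iUPD, iPR, iUPD, iPR with a best response of iPR, and iCR, iUPD, iCR with a best response of iCR.

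**3. Patient with an unconfirmed progression.** iPR at week 9; iUPD at week 18; scan at 18 + 6 = week 24 shows iPR; scan at 24 + 12 = week 36 shows iPR.
- A2.5 as written: 18 − 9 = 9 weeks, event.
- iRECIST: 36 − 9 = 27 weeks or more, censored.

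**4. The same patient with a real progression later.** As in step 3 to week 24, then iUPD at week 36, confirmed as iCPD at 36 + 6 = week 42.
- First documented progression: 18 − 9 = 9 weeks.
- iUPD that was later confirmed: 36 − 9 = 27 weeks.
- Date of iCPD: 42 − 9 = 33 weeks.

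**5. Patient who responds only after RECIST progression.** Progression/iUPD at week 9; iPR at 9 + 6 = week 15; iPR at 15 + 12 = week 27; iUPD at 27 + 9 = week 36; iCPD at week 42.
- Ending at the confirmed iUPD: 36 − 15 = 21 weeks.
- Ending at iCPD: 42 − 15 = 27 weeks.

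RECIST v1.1 reading ended at week 9, so every later event is an iUPD or an iCPD, and A2.5 names neither. By A1.10 the RECIST best response runs only until progression, so this patient is not a RECIST responder, yet the A2.5 start includes the patient.

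**The case against.** **Confirmation can be read in.** A2.5 sits in the iRECIST appendix and never says that confirmation is unnecessary. A reader who carries A2.3 into the term for progressive disease avoids the truncation. This has some force, but the nadir reference and the match with A1.8 point the other way. Even a reader who supplies confirmation still has to choose between the iUPD date and the iCPD date.

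**The start need not be pooled.** The start could be read as CR/PR for one criteria set and iCR/iPR for the other. That removes the mixing but leaves a single stop for both.

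**The listed endpoint may be RECIST only.** Section 12.3.2 uses i-prefixed terms for iRECIST response and plain PD for duration of response. On that reading A1.8 governs, and 9 weeks with an event is correct for the patient in step 3. This is a fair reading, but section 12.3.2 does not state it, and A2.5 goes beyond it by defining duration from iCR/iPR as well.

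**It belongs in the SAP.** Section 12.4 leaves further detail to the SAP, which is not shown and may settle the point. The protocol has nevertheless fixed a rule here, and that rule conflicts with A2.3.

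A reader might also infer that a patient who progresses before responding gets a negative duration, 9 − 15 = −6 weeks in step 5. That does not follow. A duration measured from response until the first progression runs forward in time, so an earlier progression cannot be its end.

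**Conclusion.** The point holds for iRECIST duration of response. As written, A2.5 closes a response at an iUPD that is not confirmed, contrary to A2.3 and A2.4.2. In the worked case this gives 9 weeks with an event instead of at least 27 weeks censored. A2.5 also leaves the end of an iRECIST-only response undefined, 21 or 27 weeks in the second case. The sequences are illustrative but follow the protocol's own schedule and tables.

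The number of patients affected cannot be derived. Section 1.1 reports that 121 of 310 patients in a cited phase II study continued past progression and that 17% of these responded. Scaled to 102 patients this is 121/310 × 0.17 × 102 = 6.8, and a reader might take that as the number with a truncated duration. It is not: those patients progressed first and responded later, which does not shorten their duration. The figure also comes from platinum-pretreated patients, whereas this trial enrols patients with stable disease after 3 to 6 cycles at first to third line. For the pattern that is truncated (response, unconfirmed progression, continued response) the protocol gives no rate. For the same reason it does not support a claim that the radiotherapy arm would be understated more.

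RECIST v1.1 duration under A1.8 is correct. The 9-week primary endpoint and the sample size are unaffected. This is a definition that should be corrected, in a secondary endpoint.

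**What to change.** Define two durations in A2.5 and section 12.3.2.
- RECIST v1.1: from first CR/PR to the first subsequent RECIST progression.
- iRECIST: from first iCR/iPR to the first subsequent iUPD that is later confirmed as iCPD, dated at that iUPD. An iUPD that is not confirmed does not end the response.

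Dating at the iUPD matches the approach in A1.7, where equivocal progression that is later confirmed takes the earlier date. Choosing the iCPD date would add 6 weeks in the worked cases, so the choice needs to be written down.

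The cost is about two sentences and one more derived variable. A2.2 already has iRECIST time-point responses recorded separately, so no new scans or data are needed. The downside is two duration figures to report instead of one.
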